## 7.1.2 Treatment-Emergent Adverse Events

Treatment-emergent AEs (TEAEs) are defined as any AEs, regardless of relationship to study drug, that have an onset or worsen in severity on or after the first dose of study drug. If it cannot be determined whether the AE is treatment-emergent due to a partial onset date, then it will be counted as a TEAE. Adverse events with incomplete start dates will be considered TEAEs, if:

- Onset time is missing but the onset date is on Study Day 1.
- Day and month are missing and the year is equal to or after the year of the first date of study drug dosing;
- Day is missing and the year is after the year of the first date of study drug dosing;
- Day is missing and the year is equal to the year of the first date of study drug dosing and the month is equal to or after the month of the first date of study drug dosing; or
- Year is missing.

#### 7.1.3 Related Adverse Events

Related AEs are those with relationship to study drug reported as "possibly related", "probably related", or "definitely related". If severity (relationship) of an AE to study drug is not recorded, the severity (relationship) will be imputed as 'severe' ('definitely related').

## 7.1.4 Summary of Treatment-Emergent Adverse Events and Serious Adverse Events

All TEAE summary tables will include the number and percentages of patients reporting TEAEs. A summary of TEAEs by severity, seriousness, and relation to study drug will be tabulated. In addition, TEAEs will be summarized by MedDRA system organ class and preferred term. Patients can have more than one TEAE per system organ class and preferred term. These summaries will include the following:

- All TEAEs
- TEAEs by worst severity
- Related TEAEs
- TEAEs leading to study drug interruption (if any)
- TEAEs leading to study drug discontinuation (if any)
- All treatment-emergent SAEs
- Treatment-emergent SAEs by worst severity
- Related treatment-emergent SAEs.

At each level of patient summarization, a patient is counted once if he/she reported one or more TEAE at that level. If a patient reported the same TEAE on multiple occasions, the highest severity (severe > moderate > mild) or study drug relationship (related > probable > possible > unlikely > unrelated) recorded for the event will be summarized. Each summary will be ordered by descending order of incidence of system organ class and preferred term within each system organ class.

## 7.2 Clinical Laboratory Evaluations

Clinical laboratory results (including chemistry, hematology, urine pH, and urine specific gravity) from the central laboratory and change from baseline will be summarized using descriptive statistics at each scheduled time point. Post-baseline laboratory assessments missing or below LLD will not be imputed, unless otherwise specified in Section 3. Box plot graphs and line graphs may be generated for selected laboratory tests, such as ALT, AST, GGT, creatine kinase (CK), and ferritin. Line graphs will include mean ± SE over time for both the observed values and for the change from baseline values.

In addition, a summary table will be provided for number and percentage of patients meeting the following pre-specified threshold level at any time during the study.

Table 5: Pre-Specified Threshold Levels for Categorical Laboratory Summaries

Lab Parameter	Pre-Specified Level
Magnesium	< 1.3 mEq/L (0.65 mmol/L)
BNP	> 200 pg/mL
ALT, AST	> 3 × upper limit of normal (ULN)
ALT, AST	> 8 × ULN
ALT, AST	> 5 × ULN for more than 2 weeks
ALT, AST, TBL	> 3 × ULN and (TBL > 2 × ULN × ULN)

Urinalysis results (other than pH and specific gravity) will not be summarized.

All laboratory results (including pregnancy test results) will be listed. Laboratory results that are above or below normal limits will be flagged in the listings.

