# 8.2. Patient Exclusion Criteria

Patients must not:

- 1. Have uncontrolled diabetes (HbA1c >11.0%)
- 2. Have B-type natriuretic peptide (BNP) level >200 pg/mL
- 3. Have a history of clinically significant left-sided heart disease and/or clinically significant cardiac disease, including but not limited to any of the following:
  - a. Clinically significant congenital or acquired valvular disease
  - b. Pericardial constriction (based on echocardiogram performed at Screening Visit or within 30 days prior to Screening Visit)

- c. Restrictive or congestive cardiomyopathy (based on echocardiogram performed at Screening Visit or within 30 days prior to Screening Visit)
- d. Symptomatic coronary disease (prior myocardial infarction, percutaneous coronary intervention, coronary artery bypass graft surgery, or angina)
- e. Evidence of left ventricular diastolic dysfunction
- f. History of atrial fibrillation
- g. History of unstable arrhythmias
- h. Cardiac insufficiency, defined as New York Heart Association Class >2
- 4. Have known active fungal, bacterial, and/or viral infection, including human immunodeficiency virus (HIV) or hepatitis virus (B or C)
- 5. Have known or suspected active drug or alcohol abuse, as per investigator judgment
- 6. Have clinically significant abnormalities of clinical hematology or biochemistry, including but not limited to elevations greater than 1.5 times the upper limit of normal of AST, ALT, or creatinine. Levels above this threshold are allowable if attributable to muscle injury
- 7. Have any abnormal laboratory test value or clinically significant pre-existing medical condition that, in the opinion of the investigator, would put the patient at risk by study enrollment
- 8. Have taken any of the following drugs within 7 days prior to Study Day 1 or plan to take any of these drugs during the time of study participation:
  - a. Sensitive substrates for cytochrome P450 2C8 or 3A4 (e.g., repaglinide, midazolam, sildenafil)
  - b. Moderate or strong inhibitors or inducers of cytochrome P450 3A4 (e.g., carbamazepine, phenytoin, ciprofloxacin, grapefruit juice)
  - c. Substrates for p-glycoprotein transporter (e.g., ambrisentan, digoxin)
- 9. Have a history of clinically significant liver disease (e.g., fibrosis, cirrhosis, hepatitis), or has, at screening, clinically relevant deviations in laboratory tests including any one of the following:

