All Day 1 procedures should be performed prior to administration of first dose of study drug.

Assessments for Visit 3 may be collected at a home health nurse visit (at appropriate locations and approved by Sponsor) or at the study center clinic.

- e Assessments for Visit 4 must be collected at the study center if patients are enrolled in Part 1 of the study. If patients are enrolled in Part 2 of the study, Visit 4 assessments may be collected by a home health nurse.
- Visit 6 should be conducted within 18 hours to 48 hours of Visit 5, and Visit 11 should be conducted within 18 hours to 48 hours of Visit 10.
- For patients with echocardiograms and electrocardiograms collected within 30 days prior to the Screening Visit, the most recent echocardiogram and electrocardiogram can be used to assess cardiac function and patient eligibility.
- At Week 2, electrocardiogram is only required for patients in Part 1 of the study.
- A home health nurse visit may be used to collect all lab samples required at the Screening Visit.
- Patients must be allowed to rest for a minimum period of 1 hour following maximal or submaximal exercise testing before this blood sample is collected (at the same time as all of the central lab blood collection). This sample must be taken prior to the 6MWT. This sample should be taken with the patient in the same position (e.g., sitting or semi-recumbent) at all appropriate visits
- Blood samples will be collected to analyze for hepatitis B and C and HIV antibodies only in patients lacking evidence of a negative titer in the past year.
- Negative serum pregnancy test results are required at the Screening Visit before study enrollment, and negative urine pregnancy test results are required at all other times indicated for continued participation in the study.
- At Week 2, study drug dispensation is only required for patients in the first cohort of Part 1 of the study.
- A dosing diary check must be performed at study drug return and pill count.
- At Week 2, study drug return, pill count, and diary check are only required for patients in the first cohort of Part 1 of the study.

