#### 3.7.2 **Definition of Study Baseline**

The average of Screening and Day 1 assessments will be used as baseline for 6MWT. For all other parameters, study baseline is defined as the last non-missing observation obtained prior to administration of the first dose on Study Day 1. Baseline will be defined as analysis visit 0.

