## 7.6 Electrocardiogram

Electrocardiogram (ECG) data, such as ventricular rate (bpm), PR interval (ms), QRS duration (ms), QT (ms), and QTc (ms) are collected on the eCRF. Descriptive statistics for observed values and change from baseline will be presented for each ECG assessment.

In addition, number and percentage of patients with any abnormal values (i.e., above a prespecified threshold) will be summarized by time point and overall while on study drug. The prespecified levels of ECG QTc thresholds are consistent with FDA guidance (See Table 6 below).

Table 6:	Pre-Specified	Threshold I	Levels for	ECG Parameters
----------	---------------	-------------	------------	----------------

ECG Parameter	Pre-Specified Level
PR	>200 msec
QTcF	>450, >480 or >500 msec, >30 or >60 msec increase from baseline
Heart rate	<40, >100 beats/min

All ECG parameters will be listed. Any results that exceed the above levels (provided in the above table) will be flagged in the listing.

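### SAP Table 5 counts laboratory exceedances over the whole study, so values from before the first dose can be charged to the assigned dose

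*SAP*

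**What the plan says.** SAP 7.2 (Clinical Laboratory Evaluations) introduces Table 5 by stating that "a summary table will be provided for number and percentage of patients meeting the following pre-specified threshold level at any time during the study". The levels are magnesium below 1.3 mEq/L, BNP above 200 pg/mL, three ALT/AST levels, and a combined ALT/AST and total bilirubin level. The section does not limit the count to values after dosing, and it plans no shift table.

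The schedule in SAP 1.2.1 places chemistry and BNP at Screening and on Day 1. A footnote adds: "All Day 1 procedures should be performed prior to administration of first dose of study drug". For laboratory parameters, SAP 3.7.2 provides that "study baseline is defined as the last non-missing observation obtained prior to administration of the first dose on Study Day 1". That baseline serves the change scores and is not applied to the Table 5 count.

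SAP 7.6 (Electrocardiogram) has a different window. Its threshold counts "will be summarized by time point and overall while on study drug". The QTcF limits in Table 6 are ">450, >480 or >500 msec, >30 or >60 msec increase from baseline". The PR limit (above 200 msec) and the heart-rate limits (below 40 or above 100 beats/min) make no reference to baseline.

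Protocol 8.2 sets the entry limits. Exclusion 2 bars BNP above 200 pg/mL. Exclusion 9 bars ALT or AST above 1.5 times ULN and bilirubin above 1.2 times ULN at screening. Exclusion 6 also uses 1.5 times ULN for ALT and AST but adds: "Levels above this threshold are allowable if attributable to muscle injury". No criterion gives a numeric limit for magnesium or PR.

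**The concern.** A table of threshold exceedances by dose is read as showing what happened on that dose. If it also counts values from before the first dose, a pre-existing abnormality appears under the assigned dose and cannot be told apart from a new one in the tabulated percentage. The SAP already avoids this for adverse events: SAP 7.1.2 requires onset or worsening on or after the first dose. The laboratory threshold table has no equivalent rule.

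Group size makes this matter. Each Part 1 cohort has 6 patients on active drug, while placebo patients are pooled over cohorts. A single pre-existing value therefore moves an active group's percentage much more than placebo's. Under SAP 1.3, Part 1 is meant to inform the choice of doses for Part 2.

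**Working it through.** **Group sizes.** SAP 1.2 and 1.3 give up to 8 cohorts of 8 patients, with 6 active and 2 placebo in each. Total: 8 × 8 = 64, which matches the SAP's figure. SAP 3.1 pools placebo: up to 8 × 2 = 16. An active group of 6 assumes that each dose is studied in one cohort.

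**Weight of one patient.**
- Active group: 1/6 = 16.7% (exact 95% interval 0.4% to 64.1%).
- Pooled placebo: 1/16 = 6.3%.

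**Which rows are exposed.** Set against the entry criteria in Protocol 8.2:
- Magnesium: no numeric entry limit, so exposed. Exclusions 6 and 7 leave it to judgment.
- ALT/AST: exclusion 9a bars values above 1.5 times ULN without exception, while exclusion 6 allows them when due to muscle injury. The two passages conflict and must be reconciled. Until they are, 9a cannot be relied on to keep such patients out. Table 5 begins at 3 times ULN, so only larger elevations count.
- BNP: the entry cut-off equals the Table 5 level, so largely protected.
- Combined row: it needs bilirubin above 2 times ULN, and entry is barred above 1.2 times ULN, so largely protected.
- Any row: a Day 1 value may pass a limit after an acceptable screen, since screening may begin 60 days before dosing.

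**Chance that a group contains at least one such patient, with no drug effect.** The documents give no prevalence *p* of pre-dose exceedance, so a range is assumed. For independent patients the probability is 1 − (1 − *p*)^n:

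| Assumed *p* | n = 6 (active) | n = 16 (pooled placebo) |
|---|---|---|
| 1% | 1 − 0.99^6 = 5.9% | 14.9% |
| 5% | 1 − 0.95^6 = 26% | 56.0% |
| 10% | 1 − 0.90^6 = 47% | 81.5% |

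Pooled placebo is more likely to contain such a patient, but each one shifts its percentage by 6.3 points rather than 16.7.

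**ECG table.** An abnormality seen only before dosing does not enter the overall on-drug count. One that persists does enter it for PR, heart rate and the absolute QTcF limits. The two QTcF increase limits are already relative to baseline.

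**Effect of separating the counts.** Take one patient in an active group whose only exceedance is before dosing. The current wording gives 1/6 (16.7%). Counting new exceedances among patients not beyond the limit at baseline gives 0/5, with the sixth patient shown separately as pre-existing. In a placebo group of 16, 1/16 becomes 0/15 in the same way.

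**The case against.** The best defence is that the phrase may not have been meant to reach back to Screening. Protocol 12.2.1.1 and 12.2.1.2 describe the study period for adverse events and pregnancies as starting at the first dose. Those passages do not govern SAP 7.2, but they make an unintended wording plausible. The wording still needs correcting, because a programmer following it would include Screening and Day 1.

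Other points limit the size of the problem, and they stand:
- Clinically significant laboratory and ECG changes must also be recorded as adverse events (Protocol 12.3 and 12.6). They are then tabulated under the treatment-emergent rule. A reader might infer that Tables 5 and 6 are the only categorical safety output for these parameters; they are not.
- All laboratory and ECG values are listed, and observed values and changes from baseline are summarized by time point. In groups this small, a pre-existing value can be traced, although the percentage itself does not separate it.
- Dose recommendations come from DSMB review. The SAP tables are planned for after the Part 1 lock, although SAP 2.2 allows earlier analyses to plan Part 2.
- SAP 1.3 says that the small groups are not expected to characterize safety fully.

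A reader might also infer that the QTc formula is undefined, because SAP 7.6 says that "QT (ms), and QTc (ms) are collected on the eCRF" while Table 6 uses QTcF. The documents do not support that as a defect. Table 6 names the Fridericia-corrected value, and the list of collected variables is given only as examples.

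**Conclusion.** The point holds for the laboratory table. On its wording, Table 5 charges pre-dose values to the assigned dose, and no other rule in the SAP prevents it. The exposed rows are magnesium, ALT/AST, and any row affected by Day 1 drift. One patient is worth 16.7 percentage points in an active group of 6. How often this would happen is unknown: the 5.9%, 26% and 47% rest on assumed prevalences of 1%, 5% and 10% and on independence between patients. The higher figures should not be applied to BNP or the combined bilirubin row, where entry criteria make a pre-dose exceedance unlikely.

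It is tempting to extend the same criticism to the ECG table. The documents do not support that, because the overall count there is already confined to time on drug and two of the QTcF limits are increases from baseline. What remains is that persisting PR, heart-rate and absolute QTcF abnormalities are not separated from new ones.

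This is a modest defect of definition in a descriptive table. It is worth correcting because the correction is simple and the groups are small.

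**What to change.** In the SAP 7.2 sentence that introduces Table 5, change the counting window to: at any time after the first dose of study drug.

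For Tables 5 and 6, show each count split by whether the patient already met that level at baseline, using the SAP 3.7.2 definition. A baseline-to-worst-post-baseline shift table would serve equally well. Either display separates new exceedances from pre-existing ones. Patients beyond a limit at baseline should not simply be dropped. Magnesium, BNP and PR each have a single level, so a patient who started beyond it and then worsened would disappear from the table.

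Separately, the sponsor should reconcile Protocol exclusions 6 and 9a on raised ALT/AST.

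The table changes cost some SAP wording and a baseline flag in the program. No new data are needed, and the only drawback is a slightly longer table.

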  - a. alanine aminotransferase (ALT) and/or aspartate aminotransferase (AST) > 1.5-fold ULN,
  - b. bilirubin > 1.2-fold ULN,
  - c. alkaline phosphatase (ALP) > 2-fold ULN,
  - d. kidney insufficiency as defined by creatinine level > 1.5 mg/dL,
  - e. albumin < lower limit of normal (LLN)
- 10. Have participated in any other interventional clinical study within 30 days prior to Study Day 1
- 11. Have a cognitive impairment that may preclude ability to comply with study procedures

- 12. Be unable to comply with the requirements of the study protocol or be unsuitable for the study for any reason, in the opinion of the investigator
- 13. Have used antioxidant supplements, including but not limited to idebenone, coenzyme Q10, nicotinamide, and vitamin E above the recommended daily allowance, within 14 days prior to Study Day 1 or plan to take any of these supplements during the time of study participation
- 14. Have taken chronic treatment with systemic corticosteroids within 30 days prior to Study Day 1
- 15. Have had significant suicidal ideation within 1 month prior to Screening Visit as per investigator judgment or any history of suicide attempts
- 16. Be pregnant or breastfeeding

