#### 3.7.4 Analysis Windows for Unscheduled Visits

Unscheduled visits will be reflected in summarization of changes to worst post-baseline measures.

Additionally, unscheduled assessments will be used in the place of missing scheduled efficacy and safety assessments, if the unscheduled assessment was collected within ±7 days of the scheduled assessment. Study day will be calculated for each unscheduled assessment and compared to the protocol defined study day for each visit. In general, analysis windows for unscheduled visits will be defined as follows:

Analysis Visit	Target Study Day	Analysis Window
0	1	Study Day ≤1
1 (Safety Only)	7	$2 \le$ Study Day $\le 10$
2 (Safety Only)	14	$11 \le $ Study Day $\le 20$
4	28	21 ≤ Study Day ≤ 35
8	56	49 ≤ Study Day ≤ 63
12	84	$77 \le \text{Study Day} \le 91$

Records from unscheduled visits that do not fall within an analysis window will be listed, but will not be analyzed.

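### The combined liver criterion in SAP Table 5 multiplies the bilirubin limit by ULN twice, so read literally its cut-off depends on the unit of measurement

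*SAP*

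**What the plan says.** SAP 7.2 plans a table giving the "number and percentage of patients meeting the following pre-specified threshold level at any time during the study". Table 5 has six rows: magnesium, BNP, three for ALT and AST, and a final one labelled ALT, AST, TBL whose level is "> 3 × ULN and (TBL > 2 × ULN × ULN", followed by a closing bracket.

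The nearby text treats limits differently:

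- The three ALT/AST rows use ULN once. One also carries its own time condition: "> 5 × ULN for more than 2 weeks".
- The magnesium row states its units, "< 1.3 mEq/L (0.65 mmol/L". The combined row states none.
- The bilirubin limit in Protocol 8.2 uses ULN once: "bilirubin > 1.2-fold ULN".

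On data handling, SAP 3.7.4 says "Unscheduled visits will be reflected in summarization of changes to worst post-baseline measures". SAP 7.2 adds that all laboratory results are listed and that "Laboratory results that are above or below normal limits will be flagged in the listings". Neither section says that bilirubin is first converted to multiples of ULN, or how an aminotransferase value is matched in time to a bilirubin value.

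**The concern.** A limit of the form k × ULN needs no stated unit, because the unit cancels when a result is divided by its ULN. A limit of the form k × ULN × ULN does not cancel. It is dimensionally invalid for bilirubin, and a program that follows it on raw values gives different answers in mg/dL and µmol/L.

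The row matters because it is the only planned criterion that adds bilirubin to the aminotransferases. Protocol 5.1 names the liver as a target organ in rats and monkeys, and reports rises in GGT, ALT, AST and total bilirubin with the adverse liver findings in rats. It also describes those rat findings as reversible and attributes the organ effects mostly to known pharmacology. Protocol exclusion criterion 6 recognises that aminotransferases can be raised by muscle injury in this population, so rows based on ALT and AST alone are harder to interpret. A count for the combined row should not depend on how a programmer resolves a malformed line.

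**Working it through.** The plan gives no expected count or numerical cut-off for this row, so there is no figure to reproduce. The check compares the literal cut-off with the presumed one.

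**Inputs.** From SAP Table 5: multiplier 2, ULN entered twice. Assumed, because the documents are silent: a bilirubin ULN of 0.8 to 1.5 mg/dL, and 17.1 µmol/L per mg/dL.

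**Formulas.** Presumed cut-off = 2 × ULN, which is 2.0 × ULN in any unit. Literal cut-off = 2 × ULN², which divided by ULN is 2 × (numeric ULN).

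| Assumed ULN | Presumed, mg/dL | Literal in mg/dL | Literal in µmol/L |
|---|---|---|---|
| 0.8 mg/dL (13.7 µmol/L) | 1.60 | 1.28 (1.6 × ULN) | 374 (27.4 × ULN) |
| 0.9 mg/dL (15.4 µmol/L) | 1.80 | 1.62 (1.8 × ULN) | 474 (30.8 × ULN) |
| 1.0 mg/dL (17.1 µmol/L) | 2.00 | 2.00 (2.0 × ULN) | 585 (34.2 × ULN) |
| 1.2 mg/dL (20.5 µmol/L) | 2.40 | 2.88 (2.4 × ULN) | 842 (41.0 × ULN) |
| 1.5 mg/dL (25.7 µmol/L) | 3.00 | 4.50 (3.0 × ULN) | 1316 (51.3 × ULN) |

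**Effect on a count, for a patient whose ALT already qualifies.**

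- *Missed in mg/dL.* ULN 1.2, TBL 2.3 × ULN = 2.76 mg/dL. This exceeds 2.40 but not 2.88, so the patient is not counted.
- *Added in mg/dL.* ULN 0.9, TBL 1.9 × ULN = 1.71 mg/dL. This exceeds 1.62 but not 1.80, so the patient is counted wrongly. It can happen only where the numeric ULN is below 1.
- *In µmol/L.* Even TBL at 10 × ULN is below every literal cut-off in the table. Here the row can only miss cases.
- *Values stored as multiples of ULN.* ULN = 1, so 2 × 1 × 1 = 2 and nothing changes.

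**Timing, as a separate check.** Take ALT at 4 × ULN on Day 14 only and TBL at 2.5 × ULN on Day 84 only, with ULN entered once. If each component is tested separately over the whole study, the patient counts. If both must be met at one visit, the patient does not. The SAP does not say which applies.

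**The case against.** The strongest reply is that nobody would program this literally. The second ULN looks like a repeated token, every comparable limit uses ULN once, and a programmer would probably read 2 × ULN or work in multiples of ULN, where the error disappears. The repetition could even have arisen when the PDF was converted to text. All of this is fair. It makes the large µmol/L figures a consequence of a literal reading, not a forecast. It does not make the written line correct, and no other text corrects it.

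The second reply is containment, and it stands too. Any patient who truly meets the combined criterion has ALT or AST above 3 × ULN and so appears in that row of the same table. All results are listed with out-of-range values flagged. The DSMB reviews unblinded safety data monthly, and the escalation and DLT rules in Protocol 7.4.2 and 7.4.3 do not use Table 5.

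Two stronger readings are tempting but unsupported:

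- A reader might infer from the label ALT, AST, TBL that the 3 × ULN condition also applies to bilirubin. The bracket gives TBL its own limit, and a 3 × requirement would make a 2 × limit redundant. The label only names the analytes involved.
- A reader might infer from "patients meeting the following pre-specified threshold level at any time during the study" that elevations at different visits must be counted together. That wording introduces all six rows. It can equally mean that the whole combined condition is met on one occasion. The text permits both readings and prescribes neither.

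**Conclusion.** The bilirubin term is wrong as written and should be corrected. Over the assumed ULN range, the literal cut-off runs from 1.6 to 3.0 × ULN in mg/dL and from about 27 to 51 × ULN in µmol/L, against a presumed 2 × ULN. These figures rest on the assumed ULN range and conversion factor, and on the row being applied literally to raw values.

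The consequence is small: one row of a descriptive Part 1 safety table could be miscounted. A reader might go further and infer that liver cases would be lost from the safety evaluation. The documents do not support that, because the aminotransferase row and the flagged listings would still show them. The missing time-pairing rule is a secondary ambiguity, which correcting the doubled ULN alone would leave in place.

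**What to change.** First check the row against the source PDF. If the second ULN is there, replace the row with: (ALT or AST > 3 × ULN) and TBL > 2 × ULN. This enters ULN once and also settles whether either or both aminotransferases must qualify.

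Then add a short statement of how the two elevations are paired: in the same sample, or within a stated number of days. Either is reasonable. A strict same-sample rule can miss a bilirubin rise at a draw shortly after the aminotransferase peak, while an unlimited window can join unrelated events. The choice should be made before the Part 1 data are analysed.

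The cost is one corrected line and one added sentence in the SAP. No new data are needed, because ALT, AST and total bilirubin are all on the planned chemistry panel (SAP Appendix 1).
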